# 11.0 TOXICITIES/SIDE EFFECTS

The National Cancer Institute (NCI) Common Terminology Criteria for Adverse Events (CTCAE) version 4.0 will be used to evaluate toxicities. Adverse events will depend on the sites receiving RT and the normal tissues adjacent to those sites.

All patients undergoing RT are likely to experience fatigue within the first several months of treatment. RT toxicities will depend on the region treated as well as the regimen. If surgery is needed on the radiated bone, patient can also be at higher risk for infection. Additional possible toxicities associated with RT include and not limited to, by site:

# **Thorax**

# Likely

- Musculoskeletal: chest wall pain
- Dermatologic: skin erythema, soft tissue edema, hyperpigmentation
- Gastrointestinal: esophagitis

# Less likely

Pulmonary: cough, shortness of breath, pneumonitis

#### Rare but serious

- Cardiac: pericardial effusion, pericarditis
- Neurosensory: transverse myelitis, brachial plexopathy
- Gastrointestinal: esophageal stenosis, perforation, fistula formation.
- Musculoskeletal: rib fractures

# Abdomen/Pelvis

#### Likely

- Dermatologic: skin erythema, soft tissue edema, hyperpigmentation
- Gastrointestinal: nausea, vomiting, diarrhea (during therapy)

# Less likely

- Hematologic: decrease in blood counts leading to infection
- Genitourinary: bladder irritation

#### Rare but serious

- Gastrointestinal: bowel ulceration, GI bleeding, fistula formation, bowel obstruction, radiation induced liver disease
- Renal: radiation nephropathy with permanent decline in renal function
- Neurosensory: transverse myelitis, brachial plexopathy

#### Spine

#### Likely

- Dermatologic: skin erythema, soft tissue edema, hyperpigmentation
- Gastrointestinal (risk depends on proximity to esophagus or bowel): esophagitis (cervical/thoracic spine), radiation laryngitis or pharyngitis (upper cervical spine), nausea and vomiting (during therapy).

# Less likely

- Pulmonary: pneumonitis (thoracic spine)
- Hematologic: decrease in blood counts leading to infection

Page **19** of **30** Version: 2/26/16

Neurosensory: pain flare

#### Rare but serious

- Musculoskeletal: vertebral body compression fracture
- Neurosensory: transverse myelitis, brachial plexopathy
- Gastrointestinal: esophageal or bowel ulceration, GI bleeding, fistula formation, bowel obstruction, esophageal perforation

# 11.1 Adverse Event Reporting

This study will use the Common Terminology Criteria for Adverse Events (CTCAE) version v4.03 for adverse event (AE) reporting. After informed consent is signed, study site personnel will record the occurrence and nature of each patient"s pre-existing conditions, including clinically significant signs and symptoms of the disease. During the study, site personnel will record any change in the pre-existing condition(s), and the occurrence and nature of any new adverse events.

All AEs related to protocol procedures are reported. All AEs occurring after the patient receives the first dose of radiation therapy must be reported in regard to their assessment of the potential relatedness of each AE to protocol procedure, studied disease state, and/or radiation modality via CRF. If a patient sradiation treatment is discontinued as a result of an AE, personnel must clearly report the circumstances and data leading to any dosage reduction or discontinuation of treatment.

Events leading to the clinical outcome of death due to disease progression will be included as part of the safety and efficacy analyses for this study.

If a death is considered related to treatment, the death should be reported as a Serious Adverse Event and appropriate guidelines followed for SAE reporting. Any clinically significant findings from labs, vital sign measurements, and other procedures should be reported as well.

## 11.2 Definitions of Adverse Events

#### 11.2.1 Adverse Event (AE)

Defined as any harm or untoward medical occurrence in a research participant administered a medical product, medical treatment or, procedure even if it does not necessarily have a causal relationship with the product, treatment, or procedure. An adverse event can be any unfavorable and unintended sign (including an abnormal laboratory finding, for example), symptom, or disease temporally associated with the use of a medical product, medical treatment, or procedure, whether or not considered to be related. Resources containing information on AEs include monthly transcripts, assessment forms obtained after each clinic visit, and hospital progress and discharge notes. Grade ≥3 adverse events other than hematologic toxicities will be recorded, graded, and reported appropriately.

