# **Secondary Objectives:**

- To compare the number of hospitalizations related to SREs between standard of care and upfront RT arms
- To compare pain-related quality of life of between standard of care and RT arms, using the Brief Pain Inventory (BPI form
- To collect health care utilities in the standard of care and RT arms using the EuroQol Group EQ-5D-5L form
- To compare pain-free survival (PFS) and overall survival (OS) between RT and standard of care arms.
- To evaluate CTCAE v4 toxicity events in the upfront RT arms.

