sum tests and established minimally important differences (MIDs) for the various measures, respectively. For scale scores with no established MIDs, the "half standard deviation" rule will be applied (i.e., differences of a half standard deviation will be considered clinically significant). At the conclusion of the study data at each time point will be presented, the number of patients in each group at a given time point will be documented, and the mean EQ-5D-5L and BPI scores for each group will be plotted over time and longitudinal pattern will be examined with the possibility of proposing more complicated regression methods such as the linear mixed models. The categorical answers (e.g., YES vs NO) from EQ-5D-5L will be compared between the two arms using Fisher"s test at each time point as well and odds ratios together with confidence intervals will be computed. Other non-quantifiable answers (e.g., treatment receiving for pain) will be summarized descriptively. For the last question in BPI, the score for pain interference on the BPI Short Form is the mean of the 7 interference questions as long as at least 4 are completed.

For comparing pain-free survival and overall survival between the two arms, both of which are time to event endpoint (time from randomization to start of opioids or death which is not necessarily within 12 months from randomization), we will use log-rank test.

To evaluate CTCAE v4 toxicity events in the upfront RT arms, we will tabulate all toxicities and summarize the CTCAE v4.03 scores and present descriptive statistics. This will be done at 3 months, 6 months, and 12 months from randomization.

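### Section 11.2.1 conflicts with Sections 10, 11.1, 11.3 and 14 on which adverse events are recorded, so the RT-arm toxicity table could be incomplete

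*Combined protocol and SAP*

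**What the plan says.** Section 11.2.1 defines an adverse event broadly, and its definition includes abnormal laboratory results. Its last sentence then reads: "Grade ≥3 adverse events other than hematologic toxicities will be recorded, graded, and reported appropriately".

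Other sections set the scope differently:

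- Section 11.1 has site staff record "the occurrence and nature of any new adverse events". It adds that "All AEs related to protocol procedures are reported" and that "All AEs occurring after the patient receives the first dose of radiation therapy must be reported", with an assessment of relatedness, on the CRF. It also asks for clinically significant laboratory findings to be reported.
- Section 11.3 has staff track any AE and enter its highest grade on the CRF.
- Section 10 schedules CTCAE assessment of Arm 2 every 5 treatment days during radiation and again at 3, 6 and 12 months.
- The secondary objective is "To evaluate CTCAE v4 toxicity events in the upfront RT arms". For it, Section 14 states "we will tabulate all toxicities and summarize the CTCAE v4.03 scores and present descriptive statistics", at 3, 6 and 12 months from randomization.

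The risk list in Section 11.0 includes "Hematologic: decrease in blood counts leading to infection" under Abdomen/Pelvis, with the same entry under Spine.

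**The concern.** Two recording rules stand side by side. One covers every AE. The other names non-hematologic events of Grade 3 or higher. A coordinator who takes 11.2.1 as the rule for the CRF would build a smaller dataset than Section 14 needs, and two coordinators could apply different rules to different patients.

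This matters more than usual here because the trial irradiates lesions that cause few or no symptoms. Lower-grade harm therefore belongs in any judgement of whether upfront treatment is worthwhile. AE evaluation is confined to Arm 2, so this one descriptive table is the planned evidence on toxicity. Omitting events can only lower its counts.

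**Working it through.** No arithmetic applies. The toxicity analysis is descriptive and depends on no alpha, power or event count. The check is a comparison of the passages by class of event, with 11.2.1 read as a limit on what is recorded.

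| Class of AE in Arm 2 | Sections 10, 11.1, 11.3 | Section 11.2.1 read as a limit | Needed for Section 14 table |
|---|---|---|---|
| Non-hematologic, Grade 3 or higher | recorded | recorded | yes |
| Non-hematologic, Grade 1-2 | recorded | not recorded | yes |
| Hematologic, any grade | recorded | not recorded | yes |

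The rules agree on the first row and differ on the other two.

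1. **Is there a precedence rule?** No. Neither Section 11 nor Section 14 says which statement governs the CRF.

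2. **Can 11.2.1 be read as covering escalated reporting alone?** Not comfortably. It speaks of recording and grading as well as reporting. Escalation is also handled elsewhere: 11.2.2 sends AEs of Grade 3 or higher to the principal investigator and IRB when relatedness is in question, 11.2.3 separates expedited from annual reporting, and 17.2 sets the serious-event rules. None of these contains a hematologic exception.

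3. **Are the omitted classes relevant to this trial?** Yes, on the protocol's own list. Section 11.0 expects fatigue in all irradiated patients. It lists skin reactions, esophagitis, nausea and vomiting as likely at one or more sites, apart from the effects it calls rare but serious. It gives no grades, so the share that would fall below Grade 3 is unknown. Decreased blood counts appear for two body regions.

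4. **Would other data fill the gap?** In part. A CBC with differential is scheduled at baseline and at 3, 6 and 12 months, and Section 11.1 gives clinically significant laboratory findings their own route. However, the Section 10 schedule has no CBC during radiation, and a laboratory value is not a graded, attributed AE until someone records it as one. No comparable back-up exists for Grade 1-2 non-hematologic events beyond the assessments whose recording is in question.

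**The case against.** The strongest reply is that 11.2.1 is a definitions section and does not forbid anything. The word *only* is absent, and the same paragraph counts abnormal laboratory results as AEs. The operative instructions in 10, 11.1 and 11.3 carry no threshold, so a careful site would record everything. On this view one loose sentence needs tidying and no data are at risk.

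Much of that stands, and it rules out several stronger readings that a reader might infer:

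- *The protocol records only Grade 3 or higher non-hematologic events.* This is a natural inference from a threshold sentence, but the text does not say it, and other sections call for the rest.
- *Lower-grade and hematologic events would never be captured.* Sections 11.1 and 11.3 provide for them, and clinically significant laboratory findings are reportable in their own right.
- *The toxicity objective cannot be met.* Even on the narrowest reading, Grade 3 or higher non-hematologic toxicity could be tabulated. The objective would be met incompletely.
- *Section 14 requires all adverse events.* It refers to all toxicities in the RT arm. The all-AE duty is in 11.1.
- *A narrow table would be published under a broad label.* Nothing in the documents supports that prediction.

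What does not stand is the claim that nothing is at risk. A sentence that names a grade and carves out a class of toxicity has little function unless it limits capture. With no precedence rule, staff could reasonably follow it.

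**Conclusion.** Wrong as written: an internal inconsistency. Section 11.2.1 cannot be squared with 10, 11.1, 11.3 and 14 on the scope of AE recording, and the passages must be reconciled.

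The consequence is conditional. If 11.2.1 is applied as the recording rule, wholly or by some staff, Grade 1-2 events and hematologic AEs would be missing or inconsistently captured. The RT-arm table would then be incomplete and could understate harm. If staff follow 11.1 and 11.3, nothing is lost. The documents do not show which happens, and they give no toxicity rates from which to estimate the loss.

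The effect is confined to one descriptive secondary objective. The primary endpoint, sample size and power are untouched. There is no between-arm toxicity comparison to bias, because Arm 1 is excluded from the scheduled follow-up AE evaluation.

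**What to change.** Delete the last sentence of 11.2.1, or reword it to say that AEs of all grades, including hematologic events found on the scheduled CBCs, are recorded and graded on the CRF in line with 11.1, 11.3 and 14.

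Leave expedited and serious-event reporting to 11.2.2, 11.2.3 and 17.2. The Grade 3 or higher non-hematologic threshold should not be turned into an expedited-reporting rule, because that would introduce a hematologic exception that those sections do not contain.

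If patients have already been treated under the current text, the report should state which recording rule was applied, since events not recorded at the time may be hard to recover.

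The cost is a wording change and slightly more CRF entry from assessments that are already scheduled.

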#### 11.2.2 Related or Possibly Related AE

An AE is "related or possibly related to the research procedures," if in the opinion of the principal investigator, it is more likely than not caused by the research procedures. AEs that are solely caused by an underlying disease, disorder, or condition of the subject, or by other circumstances unrelated to the research are not "related or possibly related". If there

Page **19** of **30** Version: 2/26/16

is any question whether or not an AE is related or possibly related, Grade 3 or higher AE should be reported to the PI and IRB.

## 11.2.3 Unexpected AE

An AE is "unexpected" when its nature (specificity), severity, or frequency are not consistent with (a) the foreseeable risk of adverse events associated with the research procedures described in protocol-related documents, such as the IRB approved research protocol, informed consent document, product labeling and package inserts, and; (b) the characteristics of the subject population being studied, including the expected natural progression of any underlying disease, disorder or condition or any predisposing risk factor profile for the adverse event. AEs that do not meet the requirement for expedited reporting will be reported to the IRB as part of the annual renewal of the protocol.

# 11.2.4 Attribution to Radiation Therapy

For reporting purposes, attribution is the assessment of the likelihood that an adverse event is caused by the research agent, or protocol intervention. The attribution is assigned by the principal investigator after considering the clinical information, the medical history of the subject, and the past experience with the research agent/intervention.

This is recorded using one of the following five categories:

- Unrelated
- Unlikely Related
- Probably Related
- Possibility Related
- Definitely Related

Related events are those which are most certainly caused by the procedures involved in the research.

Possibly related events are those which may have been caused by the procedures involved in the research.

Not related events are those which are due to an underlying disease, disorder, or condition of the subject, or due to other circumstances unrelated to the research or any underlying disease, disorder, or condition of the subject.

Unknown events are those which have an unclear relationship to the procedures involved in the research, both because more information is needed, and will be provided in follow-up, or because there is no way to make a determination.

## 11.3 Follow-up of Adverse Events

All adverse events will be followed up according to Good Clinical Practice.

During Treatment: Throughout the duration of the study, site personnel will track any change in the condition(s), the occurrence, and the nature of any AEs, and record the highest grade of the adverse event per cycle on the CRF. CTCAE grading will be assigned before each visit for any adverse events experienced during the previous visit period.

# 12.0 CRITERIA FOR THERAPEUTIC RESPONSE/OUTCOME ASSESSMENT

#### 12.1 Primary Outcome Measurement

The primary endpoint of this study is the number of skeletal related events (SREs), which will be defined as pathological fractures, spinal cord compression, or palliative radiotherapy and orthopedic surgery to bone.

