# 1.0 PROTOCOL SUMMARY AND/OR SCHEMA

[figure not shown]
Title:	A Randomized Controlled Trial of Early, Upfront Palliative Radiation versus
	Standard of Care for Highest Risk Asymptomatic or Minimally Symptomatic
	Bone Metastases
Hypothesis:	Upfront, early palliative radiation of the highest risk asymptomatic or
	minimally symptomatic (non-opioid dependent) bone metastases in patients
	will lead to fewer skeletal-related events (SREs), defined as pathological
	fractures, spinal cord compression, or palliative radiotherapy or orthopedic
	surgery to bone.
Objectives:	Primary Objective:
	To assess whether early palliative radiation of the highest risk asymptomatic/minimally symptomatic bone metastasis in patients with metastatic cancer can decrease the number of SREs, defined as pathological fractures, spinal cord compression, or palliative radiotherapy or orthopedic surgery for bone metastases.
	Secondary Objectives:
	
 
To compare the number of hospitalizations related to SREs between standard of care and upfront RT arms
 

	
 
To compare pain-related quality of life of between standard of care and RT arms, using the Brief Pain Inventory (BPI) form
 

	
 
To collect health care utilities in the standard of care and RT arms using the EuroQol Group EQ-5D-5L form
 

	
 
To compare pain-free survival (PFS) and overall survival (OS) between RT and standard of care arms.
 

	
 
To evaluate CTCAE v4 toxicity events in the upfront RT arms.
 

Patient Population:	Patients with metastatic solid tumors of metastatic disease.
Design:	Randomized, prospective trial.
Treatment	In this trial patients will be divided into 2 cohorts. Patients in Cohort 1 will
Plan:	undergo standard of care therapy for bone metastases. Patients in Cohort 2 will undergo upfront RT to ≤5 highest risk bone metastases first followed by standard of care therapy.
Number of	We plan to recruit 74 patients (see details of eligibility in the biostatistics
Patients:	section) to this protocol over 2 years.

Page **5** of **30** Version: 2/26/16

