# 2.0 OBJECTIVES AND SCIENTIFIC AIMS

# **Primary Objective:**

 To assess whether early palliative radiation of the highest risk asymptomatic or minimally symptomatic bone metastasis in patients with metastatic cancer can decrease the number of SREs, defined as pathological fractures, spinal cord compression, or palliative radiotherapy and orthopedic surgery to bone.

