#### 13.0 CRITERIA FOR REMOVAL FROM STUDY

Patients will be removed from the study if any of the following criteria are met, after review by the principal investigator:

- 1. A change in the patient's medical status unrelated to RT results in the patient being unable to comply with the protocol.
- 2. Patient is unable to continue follow-up as outlined within the protocol
- 3. Patient is found to be ineligible based on the criteria in section 6.0 of this protocol.
- 4. Patient requests to withdraw from the protocol.
- 5. Patient death.

Otherwise, patients will continue on protocol until 12 months have elapsed since date of randomization or until an SRE occurs.

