## 14.0 BIOSTATISTICS

The primary objective of this study is to compare the rate of skeletal related events (SRE) from the date of randomization to death or 12 months, whichever occurs first, between patients who received standard of care versus upfront, early palliative RT to high-risk bone metastases. We expect 60-80% of the enrolled patients can be followed for 1 year. An SRE is defined as pathological fractures, spinal cord compression, or palliative radiotherapy and orthopedic surgery for bone pain. Data suggest that the event rate is around 60% in the standard of care arm . In our institutional experience, 75% of inpatient radiation consultation led to palliative radiation for painful bone

metastasis, an SRE. Furthermore, 61% of these lesions were diagnosed at least 4 months prior to undergoing RT. We believe 60% estimated event rate at 1-year is a conservative estimate.

The primary endpoint is a binary variable and the rate refers to proportion and is defined as the number of lesions that had SRE divided by the total number of target lesions. This analysis is lesion-based so an SRE (or no SRE) at one site does not affect the status of other sites from the same patient. We estimate that the investigational arm has the event rate around 30%. Radiation therapy is extremely effective in alleviating pain due to bone metastases with 70-80% pain control. By preventing the development of significant bone pain, which often leads to SREs, RT can effectively reduce SREs, To this end we will analyze at least 66 patients with valid SRE endpoint (randomized 1:1 to each arm) to achieve >80% power in detecting such a difference using a two-sample, one-sided proportion test with alpha<0.05. Since patients who withdraw before the endpoint can be evaluated will not be included in the analysis (i.e., it will NOT be an intent-to-treat analysis) we will over-accrue to account for withdrawals to ensure a minimum of 33 patients in each arm (subject to stratification, see Section 15.2) who can contribute the analyzable endpoint of SRE. We believe an additional 10% would be sufficient so totally we expect to randomize 74 patients. A small portion of patients (<15%) may have multiple lesions, in which case they will be treated as independent analysis units. In other words, the eventual effect sample size may be slightly higher than 66 because this objective will be analyzed per lesion.

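### The primary endpoint is a number of SREs in Section 12.1 but a yes/no outcome per target lesion in Section 14, and Section 13's stop at an SRE contradicts Section 14's follow-up window

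*Combined protocol and SAP*

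**What the plan says.** Four parts of the combined protocol and SAP bear on the primary endpoint.

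- **Sections 1.0 and 2.0 (objective).** Section 1.0 asks whether early radiation of the highest-risk lesions "can decrease the number of SREs, defined as pathological fractures, spinal cord compression" and the other listed event types. Section 2.0 has the same aim, that it "can decrease the number of SREs". Both are objectives. Neither gives a unit.
- **Section 12.1 (endpoint).** "The primary endpoint of this study is the number of skeletal related events (SREs", followed by the list of event types. It does not say whether the number is per patient or per lesion, which bones count, or how a second event at the same site is handled.
- **Section 14.0 (analysis).** The aim is to "compare the rate of skeletal related events (SRE) from the date of randomization to death or 12 months, whichever occurs first". Then: "The primary endpoint is a binary variable and the rate refers to proportion", and it is "defined as the number of lesions that had SRE divided by the total number of target lesions". The section adds that "this objective will be analyzed per lesion" and that what happens at one site leaves the status of the patient's other sites unchanged. It sets a one-sided two-sample proportion test, 60% against 30%, with 66 evaluable and 74 randomized patients.
- **Section 13.0 (time on protocol).** Patients who are not removed for another reason continue "until 12 months have elapsed since date of randomization or until an SRE occurs".

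Section 4.1 has physicians list up to five highest-risk bone lesions at randomization, in both arms, for follow-up.

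**The concern.** Sections 12.1 and 14 each state what the primary endpoint is, and they describe different quantities. A number of SREs rises with every further event. A lesion-level yes/no does not change after the first event at that lesion and never registers an event elsewhere. No section says which statement governs.

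What is at stake is the claim the trial can make. The hypothesis in Section 1.0 is about fewer SREs. A positive Section 14 result shows that a smaller share of the listed lesions had an SRE, which is narrower than a fall in the SREs that a patient experiences.

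Section 13 adds a data problem. Section 14 needs every target lesion observed to death or 12 months, whatever happens at other sites. A rule that takes the patient off protocol when an SRE occurs would stop that observation for the lesions still at risk.

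**Working it through.** **1. Which definition the sample size belongs to.** Inputs from Section 14: p1 = 0.60, p2 = 0.30, one-sided alpha 0.05 (z = 1.645), power 80% (z = 0.842), 1:1 allocation.

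n per arm = [1.645·√(2·0.45·0.55) + 0.842·√(0.60·0.40 + 0.30·0.70)]² / 0.30² = 32.9, so 33 per arm and 66 in total. Power at 33 per arm is 80.1%. Allowing for 10% withdrawal, 66/0.90 = 73.3, so 74.

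The plan's figures reproduce exactly, for the binary proportion only. The documents give no mean count, dispersion or test for a number of SREs, so no sample size can be computed for that version.

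**2. Where the two definitions part.** They agree only if no target lesion has more than one SRE, no SRE occurs outside the target lesions, and the arms have equal numbers of lesions.

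Hypothetical example, assuming all events are recorded to 12 months: 20 of 33 control lesions have one SRE each, and 10 of 33 radiation-arm lesions have two each.

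- Section 14: 61% against 30%. The pooled proportion is 30/66 = 0.455 and the standard error is √(0.455·0.545·2/33) = 0.1226, so z = 0.303/0.1226 = 2.47 and one-sided p = 0.007.
- Section 12.1: 20 SREs against 20, no difference.

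If follow-up really stopped at an SRE, as Section 13 says, the second events would not be recorded. The example shows how the definitions differ, not what the trial would observe.

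**3. How much off-target events could matter (assumed inputs).** The documents give no off-target rate, so a range is used. Each simulated patient has one target lesion, with 33 patients per arm, 60% against 30% of lesions affected once, the same mean number of off-target SREs in both arms, one-sided 0.05, and 2,000 simulated trials per row. The count is compared by a Wilcoxon rank sum test, which the plan does not specify for SREs.

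| Assumed off-target SREs per patient | Power, lesion proportion | Power, SREs per patient | Tests disagree |
|---|---|---|---|
| 0 | about 80% | about 79% | 0% |
| 0.5 | about 80% | 44% | 42% |
| 1 | about 80% | 32% | 54% |
| 2 | about 80% | 20% | 65% |

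These rows show how sensitive the count is. They do not estimate the divergence in this trial.

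**4. What Section 13, read literally, leaves unobserved under Section 14.**

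- One target lesion, first SRE at that lesion: the binary outcome is settled and nothing is lost.
- One target lesion, first SRE elsewhere: the target lesion is observed only to that date.
- Several target lesions, first SRE at any site: the target lesions still event-free are observed only to that date.
- No SRE: observed to death or 12 months, as intended.

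Section 14 expects fewer than 15% of patients to have several lesions: 0.15 × 66 = 9.9, so at most 9 evaluable patients, or 0.15 × 74 = 11.1, so at most 11 randomized. The documents give no figure for patients whose first SRE is off-target. Nor do they say whether a lesion cut short in this way counts as event-free or as not evaluable.

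**5. Secondary endpoints.** Section 14 defines these, unless otherwise specified, from randomization to death or 12 months, including SRE-related hospitalizations. Section 10.0 schedules pain and utility questionnaires for all patients at 3, 6 and 12 months. A stop at an SRE cuts both short.

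**The case against.** The best reply is that Section 14 is simply the operational form of a loosely worded endpoint. Its numerator is itself a number of lesions with an SRE, it alone has a test and a sample size, and the lesions are named at randomization. Much of this stands. The planned analysis is clear and its arithmetic is right. What remains is that Section 12.1 names a different quantity as the primary endpoint and nothing gives Section 14 precedence.

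On Section 13, it can be said that leaving the protocol need not end data collection. Section 14 gives a window to death or 12 months, and it lets pain-free and overall survival run past 12 months. That may be the intent, but Section 13 makes no exception for outcome data.

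Several stronger readings are tempting, and the documents do not support them.

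- *Sections 1.0 and 2.0 define a per-patient count.* They state an objective without a unit. The contradiction rests on Section 12.1.
- *The analysis cannot support the hypothesis.* The hypothesis concerns radiation of the highest-risk lesions, and a lower proportion of those lesions with an SRE is direct evidence about them. The limit is on extending it to a patient's total SREs.
- *More than five metastatic sites against at most five targets guarantees untreated bone lesions.* The eligibility criterion in Section 6.1 does not require the sites to be in bone. Off-target SREs are possible but not established.
- *Section 13 defeats capture of the endpoint altogether.* A patient with one target lesion whose first SRE is there is fully captured under Section 14.
- *The sponsor could choose between two analyses after seeing the data.* Only the binary one is specified, so a switch would be a visible departure from Section 14.

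**Conclusion.** The concern holds as a conflict of definition together with a conflicting follow-up rule. It is not a calculation error. Section 12.1 and Section 14 state different primary endpoints, and the 33, 66 and 74 belong to the Section 14 version. A lower target-lesion proportion would not by itself show fewer SREs per patient.

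How far the two could diverge cannot be derived from the documents, because they give no rate of repeat or off-target SREs. The simulated figures depend wholly on the assumed rates.

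The Section 13 conflict depends on reading its stopping clause literally. On that reading the Section 14 endpoint is incomplete for patients with several target lesions (at most 9 of 66 if the plan's under-15% expectation is right), and for an unknown number whose first SRE is off-target. The 12-month secondary endpoints are also cut short. This should be corrected, but it does not invalidate the planned analysis.

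**What to change.** - **Section 12.1:** state the Section 14 endpoint, namely SRE yes or no at each target lesion listed at randomization, from randomization to death or 12 months, whichever is first.
- **Sections 1.0 and 2.0:** word the hypothesis and primary objective to refer to SREs at those target lesions, so that the claim matches the analysis.
- **Section 13.0:** remove the stop at an SRE for outcome data collection, so that all target lesions and the 12-month secondary outcomes are followed to death or 12 months.
- **Optional:** report total SREs per patient, at all sites, as a descriptive secondary outcome.

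The cost is wording changes and some further chart follow-up after a first SRE. The planned sample size does not change. If the sponsor intends the count as primary, a count-based test and a new sample size would be needed instead.
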